5.0 SUBJECT SELECTION AND WITHDRAWAL

5.1 Subject Population

This trial will enroll Russian subjects with symptomatic chronic severe DMR and FMR per the MitraClip NT System IFU. Subjects must meet all eligibility criteria and provide written informed consent prior to conducting any investigation-specific procedures not considered standard of care.

5.2 Subject Screening

5.2.1 Subject Screening

The Principal Investigator at the site is responsible for screening subjects for the **MitraClip NT System** Russian Trial. All subjects must have a documented in-person consultation with the Cardiothoracic (CT) Surgeon investigator to assess surgical risk. The **MitraClip NT** implanter (who may also be the Principal Investigator) and a physician trained in echocardiography will also assess suitability of the subject for eligibility in the trial. These assessments combined are referred to as Site Heart Team. Refer below to the Table 1 for responsibilities.

Table 1. Responsibilities

| Role / Specialty | Responsibility |
|-----------------------------|--|
| Interventional Cardiologist | 
• Local Site Heart Team Member |

Abbott

CT Surgeon

- Screens potential subjects
- Performs **MitraClip NT** procedure*
- Local Site Heart Team Member
- Provides in-person assessment of surgical difficulty
- Local Site Heart Team Member
- Evaluates potential subjects for echocardiographic eligibility criteria
- Participates in the **MitraClip NT** procedure
- Perform required analysis of the TEE & TTE to complete the Case Report Form (CRF)

Potential patients will be fully informed about the clinical investigation, following the established Informed Consent process (described in [Section 5.2.2]). Once a duly dated and signed Informed Consent form is obtained, the clinical investigation-specific screening procedures may begin.

Subjects must be screened for clinical investigation eligibility by a member of the site's clinical investigation team previously trained to the CIP, and if applicable will be entered into a site-specific screening log.

In case the subject does not meet all inclusion criteria or meets any of the exclusion criteria, the subject is considered a screening failure. The Principal Investigator or the delegated clinical investigation personnel will record the screening failure in the hospital records and on a screening log as required.

Subject data will be collected following enrollment into the clinical investigation.

5.2.2 Informed Consent

The Investigator or his/her authorized designee (if applicable) will conduct the Informed Consent process, as required by applicable regulations and the center's IRB/EC. This process will include a verbal discussion with the subject on all aspects of the clinical investigation that are relevant to the subject's decision to participate, such as details of clinical investigation procedures, anticipated benefits, and potential risks of clinical investigation participation. Subjects must be informed about their right to withdraw from the clinical investigation at any time and for any reason without sanction, penalty or loss of benefits to which the subject is otherwise entitled. Withdrawal from the clinical investigation will not jeopardize their future medical care or relationship with the investigator.

During the discussion, the Principal Investigator or his/her authorized designee will avoid any improper influence on the subject and will respect subject's legal rights. Financial incentives will not be given to the subject. Subjects may be compensated for time and travel directly related to the participation in the clinical investigation. The subject shall be provided with the Informed Consent form written in a language that is understandable to the subject and has been approved by the center's IRB/EC. The subject shall have adequate time to review, ask questions, and consider participation. The Principal Investigator or his/her authorized designee will make efforts to ensure that the subject understands the information provided. If the subject agrees to participate, the Informed Consent form must be signed and dated by the subject and

Abbott

thereafter by the person obtaining the consent prior to any clinical investigation-specific procedures. The signed original will be filed in the subject's hospital or research charts, and a copy will be provided to the subject.

Failure to obtain informed consent from a subject prior to clinical investigation enrollment should be reported to Sponsor within 5 working days and to the reviewing center's IRB/EC according to the IRB's/ EC's reporting requirements.

If, during the clinical investigation, new information becomes available that can significantly affect a subject's future health and medical care, the Principal Investigator or his/her authorized designee (if applicable) will provide this information to the subject. If relevant, the subject will be asked to confirm their continuing informed consent in writing.

5.2.2.1 Special Circumstances for Informed Consent

Incapacitated subjects defined as mentally ill, mentally handicapped, or individuals without legal authority may be enrolled in this clinical investigation, as data of comparable validity cannot be obtained from clinical research involving only persons able to give informed consent or by other research methods. Additionally, the clinical investigation directly relates to a medical condition from which the individual suffers, and the clinical investigation is expected to produce a direct benefit to the individual, outweighing the risks and burdens involved.

Individuals under the age of 18 or age of legal consent are excluded from the study population.

Individuals unable to read or write may be enrolled in this clinical investigation.

Informed consent will be obtained through a supervised oral process. An independent witness will be present throughout the Informed Consent process. The written Informed Consent form and any other information will be read aloud and explained to the prospective subject or his/her legally acceptable representative and either will sign and personally date the Informed Consent form. The witness will also sign and personally date the Informed Consent form attesting that the information was accurately explained and that informed consent was freely given.

Pregnant or breastfeeding women are excluded from the study population.

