5.3.3 Exclusion Criteria

5.3.3.1 General Exclusion Criteria

1. Subject is currently participating in another clinical investigation.
2. Pregnant or nursing subjects and those who plan pregnancy during the clinical investigation follow-up period.
3. Patients with the following conditions:
 - Patients who cannot tolerate procedural anticoagulation or post procedural anti-platelet regimen;
 - Active endocarditis of the mitral valve;
 - Rheumatic mitral valve disease;
 - Evidence of intracardiac, inferior vena cava (IVC) or femoral venous thrombus.
4. Contraindications for reusable accessories (stabilizer, lift, support plate).

Abbott

5. Presence of other anatomic or comorbid conditions, or other medical, social, or psychological conditions that, in the investigator's opinion, could limit the subject's ability to participate in the clinical investigation or to comply with follow-up requirements, or impact the scientific soundness of the clinical investigation results.

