5.4 Subject Enrollment

A patient is considered enrolled in the clinical investigation from the moment the patient provides written informed consent

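### Section 5.2.2.1 admits incapacitated subjects on a claim of necessity that nothing else in the CIP supports, and the consent rules do not settle who signs for them

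*Protocol*

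**What the plan says.** Protocol Section 5.2.2.1 (Special Circumstances for Informed Consent) states: "Incapacitated subjects defined as mentally ill, mentally handicapped, or individuals without legal authority may be enrolled in this clinical investigation". It gives three grounds. The first is necessity: "as data of comparable validity cannot be obtained from clinical research involving only persons able to give informed consent", or by other research methods. The other two are that the study relates to a condition the person has, and that a direct benefit outweighing the risks and burdens is expected.

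The section then excludes minors, admits people who cannot read or write, and describes a supervised oral process with an independent witness. In that process the form is read and explained to the "prospective subject or his/her legally acceptable representative and either will sign and personally date the Informed Consent form". The witness signs and dates it as well. Pregnant and breastfeeding women are excluded.

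The general rules elsewhere are worded for the subject alone:

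- Section 5.1: "Subjects must meet all eligibility criteria and provide written informed consent prior to conducting any investigation-specific procedures" outside standard of care.
- Section 5.2.2: "the Informed Consent form must be signed and dated by the subject", and then by the person obtaining consent.
- Section 5.4: "A patient is considered enrolled in the clinical investigation from the moment the patient provides written informed consent".

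None of the three names a representative or refers to Section 5.2.2.1.

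**The concern.** Enrolling people who cannot consent needs a reason specific to the study and a consent route that a site can follow without guessing. Here the reason is asserted without support, and the route is unclear.

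What is at stake is protection of the subject. The procedure is done under general anaesthesia and leaves up to two permanent clips in place. Table 4 schedules transoesophageal echocardiography at baseline, discharge and 10 days, and Section 6.1 requires a further one within 3 days before the procedure. Every subject carries this burden. The question is whether someone unable to agree to it should carry it in a study that does not need that group.

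There is a secondary consequence for the analysis. Section 5.4 ties enrolment to the patient's own written consent. Section 5.4.1 places registration after enrolment, and Protocol Section 8.1 and SAP Section 2.1.1 define the analysis population through registration. For a subject whose representative signed, the text does not settle the first link in that chain.

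**Working it through.** No formula applies and the plan states no figure on this point, so the check is a comparison of the relevant sections.

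**1. Is the necessity supported anywhere?**

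- Objective (Protocol 2.1, SAP 1.2): safety and effectiveness for mitral regurgitation in the Russian population. Incapacity is not mentioned.
- Eligibility (5.3.2.1, 5.3.3.1): no criterion selects for incapacity or refers to it.
- Endpoints (4.1, 4.2): none concerns incapacity.
- Analyses (Protocol 8.3 and 8.5, SAP 2.6): descriptive only, with no subgroups.
- Section 1.0: the predicted treatment result, both efficacy and safety, is listed among the properties already evaluated in earlier studies.
- Section 2.2.4: the five studies summarised total 55 + 279 + 78 + 899 + 614 = 1,925 subjects, not counting 51 roll-in subjects in the COAPT trial. The summaries do not say that incapacitated subjects were needed, and do not report any subject's capacity to consent.

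The necessity is therefore unsupported. The other two grounds concern benefit to the individual. They do not show why persons able to consent could not provide the data.

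**2. Do the consent rules fit together?**

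| Section | Whose consent or signature | Exception stated |
|---|---|---|
| 5.1 | Subject | None |
| 5.2.2 | Subject, then the person obtaining consent | None |
| 5.4 | Patient | None |
| 5.2.2.1, oral process | Subject or representative, plus witness | Scope not stated |

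Under Section 5.2.2, failure to obtain consent from a subject before enrolment must be reported to the sponsor within 5 working days. A form signed only by a representative could be read as valid under 5.2.2.1 or as a reportable failure under 5.2.2. The re-consent text in 5.2.2 also asks only the subject to confirm.

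**3. Does the representative route cover incapacitated subjects?**

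The oral-process text directly follows the sentence on people who cannot read or write, and is separated from the incapacity paragraph by the exclusion of minors. Two readings are open: that it serves only people who cannot read or write, or that it serves both groups. On the first reading, incapacitated subjects have no described route at all.

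**4. Who signs, on the wider reading?**

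The text says "either will sign and personally date the Informed Consent form" and gives no rule for choosing. An incapacitated person's own signature, with the witness's, could then be taken as consent. Equally, a representative could sign for a capable adult whose only difficulty is reading.

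**5. Is there a check before signature?**

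The group is defined by diagnosis or legal status. No assessment of capacity and no assent step is described.

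**The case against.** The strongest reply is structural. Section 5.2.2.1 sits under 5.2.2 and is headed as a special case, so departing from the general signature rule is what it is for. It names a legally acceptable representative, which suits incapacitated subjects better than capable adults who cannot read. It requires an independent witness throughout, who also signs. The Compliance Statement binds sites to the Declaration of Helsinki, ISO 14155:2011 and local law, with the strictest requirement prevailing. Section 12.0 requires ethics-committee approval of the plan and consent form before anyone is consented. Exclusion 5 reaches "Presence of other anatomic or comorbid conditions, or other medical, social, or psychological conditions that", in the investigator's opinion, could limit participation, compliance or scientific soundness.

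Much of this stands, and it rules out four stronger readings that a reader might infer:

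- *That the protocol's own evidence contradicts the justification.* Section 2.2.4 never gives the consent capacity of earlier subjects, so it can only fail to support the claim.
- *That 5.2.2.1 breaks the protocol's own signature rules.* A special provision may depart from a general one. The defect is that the sections are not reconciled.
- *That an incapacitated person may sign alone.* In the oral process a witness also signs, and 5.2.2 adds the person obtaining consent.
- *That each such subject puts 1/16 = 6.25 percentage points of every rate at risk.* Nothing says the data would become unusable. If one subject were removed, the denominator would become 15. A rate of 16/16 would become 15/15, with no change. Removing a non-success from x/16 gives x/15, a shift of x/15 − x/16 = x/240. Removing a success gives (x − 1)/15, a shift of −(16 − x)/240. Either reaches 6.25 points only at the extreme (x = 15 or x = 1 respectively).

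The reply does not supply a reason for the necessity, a statement of whom the representative route covers, or a rule on who signs. The general commitments apply to any trial and do not settle these points. Exclusion 5 is discretionary and does not name incapacity.

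**Conclusion.** The point holds as a matter of subject protection and should be acted on. The protocol permits enrolment of people who cannot consent, on a necessity that nothing else in it supports. It leaves unclear whether a representative must act for them, and describes no capacity assessment or assent. A site could in good faith take an incapacitated person's witnessed signature as sufficient.

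No numerical effect can be given. The documents do not say how many such subjects might be expected among the 16, or what would happen to their data if consent were challenged. The conclusion assumes that the supplied text is complete on this point. A consent form or site procedure outside these documents might contain further safeguards, but the protocol would still need to agree with it.

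**What to change.** **Preferred.** Delete the paragraph in Section 5.2.2.1 that permits incapacitated subjects. Add an exclusion to Section 5.3.3.1, for example: *Subject lacks the capacity or legal authority to give informed consent.* For capable subjects who cannot read or write, keep the witnessed oral process, but replace the either-may-sign wording with a requirement that the subject signs or marks the form together with the witness.

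**Alternative, if the sponsor keeps the group.** State why this study needs incapacitated subjects. Require a documented capacity assessment, then the legally acceptable representative's signature together with the subject's assent. Add matching wording or cross-references to Sections 5.1, 5.2.2 (including reporting of missing consent and re-consent) and 5.4, so that these sections and 5.2.2.1 agree.

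**Cost.** Either option is an amendment to the protocol and consent wording, with ethics-committee approval. The sample size, endpoints and analyses are unchanged. Under the preferred option an occasional otherwise eligible patient is not enrolled. The documents give no figure for how often that would happen.

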5.3 Eligibility Criteria

5.3.1 General Eligibility Criteria

Assessment for general eligibility criteria is based on medical records of the site and interview with a candidate patient. If some of the clinical and laboratory tests are not included in site standard tests, they must be done but after written informed consent is obtained. Patients must meet ALL of the inclusion criteria to be

Abbott

considered for the clinical investigation. If ANY of the exclusion criteria are met, the patient is excluded from the clinical investigation and cannot be enrolled.

5.3.2 Inclusion Criteria

5.3.2.1 General Inclusion Criteria

- Age 18 years or older.
- Symptomatic moderate-to-severe (3+) or severe MR (4+) chronic DMR or FMR determined by assessment of a qualifying transthoracic echocardiogram (TTE) obtained within 90 days or transesophageal echocardiogram (TEE) obtained within 180 days prior to subject registration.
 - LVEF \geq 30%
 - NYHA classification is class II, class III, or ambulatory class IV.
 - Subject is deemed difficult for mitral valve surgery due to either STS surgical mortality risk for mitral valve replacement of \geq 8% OR due to the presence of one of the following risk factors:
 - Porcelain aorta or mobile ascending aortic atheroma
 - Post-radiation mediastinum
 - Previous mediastinitis
 - Functional MR with LVEF $<$ 40%
 - Over 75 years old with LVEF $<$ 40%
 - Re-operation with patent grafts
 - Two or more prior cardiothoracic surgeries
 - Hepatic cirrhosis
 - Other surgical risk factor(s)
 - Mitral valve area \geq 4.0 cm².
 - The primary regurgitant jet is non-commisural, and in the opinion of the implanting investigator can successfully be treated by the MitraClip NT System. If a secondary jet exists, it must be considered clinically insignificant.

5.3.3 Exclusion Criteria

5.3.3.1 General Exclusion Criteria

1. Subject is currently participating in another clinical investigation.
2. Pregnant or nursing subjects and those who plan pregnancy during the clinical investigation follow-up period.
3. Patients with the following conditions:
 - Patients who cannot tolerate procedural anticoagulation or post procedural anti-platelet regimen;
 - Active endocarditis of the mitral valve;
 - Rheumatic mitral valve disease;
 - Evidence of intracardiac, inferior vena cava (IVC) or femoral venous thrombus.
4. Contraindications for reusable accessories (stabilizer, lift, support plate).

Abbott

5. Presence of other anatomic or comorbid conditions, or other medical, social, or psychological conditions that, in the investigator's opinion, could limit the subject's ability to participate in the clinical investigation or to comply with follow-up requirements, or impact the scientific soundness of the clinical investigation results.

5.4 Subject Enrollment

A patient is considered enrolled in the clinical investigation from the moment the patient provides written informed consent

5.4.1 Subject Registration

A subject is considered registered when after enrolment and screening procedures it has been confirmed that the subject meets all inclusion criteria and none of the exclusion criteria and upon femoral vein puncture for transseptal access in preparation for the **MitraClip NT System** insertion.

5.6 Subject Withdrawal

Each enrolled subject shall remain in the clinical investigation until completion of the required follow-up period; however, a subject's participation in any clinical investigation is voluntary and the subject has the right to withdraw at any time without penalty or loss of benefit. Conceivable reasons for discontinuation may include, but not be limited to, the following:

- Subject death
- Subject voluntary withdrawal
- Subject lost-to follow-up as described below
- Subject's follow-up is terminated according to Section 3.1.

The Sponsor must be notified of the reason(s) for subject discontinuation. The site will provide this information to the Sponsor. Investigators must also report this to their respective IRB/EC as defined by their institution's procedure(s).

No additional follow-up will be required or data recorded from subjects once withdrawn from the clinical investigation, except for the status (deceased/alive).

However, if a subject withdraws from the investigation due to problems related to the safety or performance of the device under investigation, the investigator shall ask for the subject's permission to follow his/her status/condition outside of the clinical investigation.

Lost-to-Follow-up

If the subject misses two consecutive scheduled follow-up time points and the attempts at contacting the subject detailed below are unsuccessful, then the subject is considered lost-to-follow-up. Site personnel shall

Abbott

make all reasonable efforts to locate and communicate with the subject (and document these efforts in the source documents), including the following, at each contact time point:

- A minimum of two telephone calls on different days over the specified follow-up windows to contact the subject should be recorded in the source documentation, including date, time and initials of site personnel trying to make contact.
- If these attempts are unsuccessful, a letter (certified if applicable) should be sent to the subject.
- If a subject misses one or more non-consecutive follow-up contact time points, it will be considered a missed visit. The subject may then return for subsequent visits. If the subject misses two consecutive time points and the above-mentioned attempts at communicating with the subject are unsuccessful, the subject will be considered lost-to-follow-up.

Note: Telephone contact with General Practitioner, non-clinical investigation cardiologist or relative without the presence of the subject or indirect documentation obtained via discharge letters will not be considered as subject contact.

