5.7 Number of Subjects

Sixteen (16) subjects will be registered in the clinical investigation.

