## 2.0 ANALYSIS CONSIDERATIONS

### 2.1 Analysis Populations

#### 2.1.1 Attempted Procedure Population (ATP)

FMR or DMR Russian patients who meet the eligibility criteria for the MitraClip NT System Instructions for Use (IFU) in Russia and registered into the study.

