#### 2.3.2 Descriptive Endpoints

The analyses for the descriptive endpoints will be performed using the methods described in Section 2.2 for ATP populations.

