## Statistical Analysis Plan

### 2.7 Handling of Missing Data

All analyses will be based on available data with missing data excluded. Any unused or spurious data will be noted as appropriate in the final report.

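### Non-fatal events after withdrawal are not trial data, and a missed day-30 visit prompts no vital-status check, so the 30-day results may be optimistic

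*Protocol*

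**What the plan says.** - **After withdrawal (Protocol 5.6).** "No additional follow-up will be required or data recorded from subjects once withdrawn from the clinical investigation, except for the status (deceased/alive". For a subject leaving because of device safety or performance, "the investigator shall ask for the subject's permission to follow his/her status/condition outside of the clinical investigation".
- **Safety surveillance (Protocol 7.3.1).** Surveillance ends at withdrawal, among other end points. The same section also says adverse events are collected on every subject up to the 30-day visit.
- **Missed visits (Protocol 5.6).** Loss to follow-up starts from this condition: "If the subject misses two consecutive scheduled follow-up time points". One missed visit is only a missed visit. At least two calls and then a letter are required at each time point. Information from a relative, a general practitioner or a discharge letter "will not be considered as subject contact".
- **Schedule (Protocol 5.8 and 6.1).** Visits are at discharge, day 10 and day 30, and the subject leaves the trial after day 30.
- **Analysis (SAP).** Section 2.7: "All analyses will be based on available data with missing data excluded". The ATP in 2.1.1 is the eligible patients "in Russia and registered into the study", and 2.3.2 analyses the descriptive endpoints "using the methods described in Section 2.2 for ATP populations".
- **Size (Protocol 5.7).** "Sixteen (16) subjects will be registered in the clinical investigation".

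**The concern.** A subject who leaves because of a device problem is plausibly at higher risk of re-intervention, readmission or a further device-related SAE before day 30. The plan foresees following such subjects with their permission, yet places what is learned outside the trial. A second group is affected too. A subject who attends day 10 but cannot be reached at day 30 has no later visit at which to reappear, and nothing requires the site to establish whether that person is alive, although vital status is kept for subjects who formally withdraw.

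At stake are the 30-day descriptive endpoints: Device Success, Procedural Success, hospitalization and SAEs, plus mortality for the subject missing only day 30. The stated objective is safety and effectiveness, and the follow-up is one month. For scale only, since eligibility differs, Protocol 2.2.4 reports 30-day figures of 7.7% mortality and 26.9% major adverse events for the EVEREST II High Risk Registry. In 16 subjects that is 16 × 0.077 = 1.2 deaths and 16 × 0.269 = 4.3 subjects with events. Against counts that small, one or two unrecorded cases would be visible.

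**Working it through.** **No plan figure to reproduce.** The study has no hypothesis test (Protocol 8.3), the sample-size reasoning is redacted, and the readable text gives no withdrawal or loss rate. The check therefore traces what is recorded and then bounds the effect.

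**Step 1. What is kept and what is lost.**

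| Subject | Kept | Not required or not recorded |
|---|---|---|
| Withdraws over a device problem, gives permission | ATP membership; adverse events up to withdrawal (7.3.1); full assessments before leaving (6.1); vital status afterwards (5.6) | Non-fatal events and re-interventions from withdrawal to day 30 |
| Attends day 10, not reached at day 30 | ATP membership; data to day 10; calls and a letter | Vital status and hospitalizations to day 30; day-30 echo |

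For example, a subject who withdraws on day 12 and is re-operated on day 20 has no trial record of the re-operation.

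**Step 2. How SAP 2.7 meets this.** Device Success (SAP 1.4.2) needs the intended clips in place, MR reduced to mild or less, no re-intervention and no device-related SAE. Without day-30 data it cannot be scored as a success. The primary endpoint has an explicit failure rule for death or surgery before discharge (SAP 1.4.1). The 30-day composites have no rule for incomplete components. Where a failing component is already known but the day-30 echo is missing, the SAP does not say whether the subject is a failure or is left out.

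**Step 3. Size.** Let k of the 16 subjects have no day-30 result, and let s be the successes among the other 16 − k.

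- Available-case rate: s/(16 − k).
- Rate if all k truly failed: s/16.
- Overstatement: s/(16 − k) − s/16 = s·k/[16(16 − k)]. This is largest when s = 16 − k, where it equals k/16.

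The values of k are assumed. With no other failures, and exact 95% intervals:

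| k | Available case | Missing counted as failure | Overstatement |
|---|---|---|---|
| 1 | 15/15 = 100% (lower limit 78.2%) | 15/16 = 93.75% (69.8 to 99.8) | 6.25 points |
| 2 | 14/14 = 100% (lower limit 76.8%) | 14/16 = 87.5% (61.7 to 98.4) | 12.5 points |
| 3 | 13/13 = 100% (lower limit 75.3%) | 13/16 = 81.25% (54.4 to 96.0) | 18.75 points |

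**Step 4. Other directions.** Take k = 2 with four observed failures, so s = 10. The available-case rate is 10/14 = 71.4%. If both missing subjects failed, the full rate is 10/16 = 62.5% and the overstatement is 8.9 points. If both succeeded, it is 12/16 = 75.0% and the available-case rate is 3.6 points too low.

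**Step 5. An event known before withdrawal.** If one device-related SAE is counted, the rate is 1/16 = 6.25% (0.2 to 30.2). It becomes 0/15 (0 to 21.8) only if the whole subject is dropped, which no section directs.

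**The case against.** A reader might infer that Section 5.6 keeps device-problem leavers, or subjects who miss the last visit, out of the 30-day safety results, and that those results are therefore biased in favour of the device. The documents do not support this.

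- Section 5.6 limits what is recorded. It removes nobody from the ATP.
- The device problem that prompts a withdrawal comes before it. It falls within adverse event collection (Protocol 7.3.1) and device deficiency reporting (7.3.3), and the reason for leaving goes to the sponsor (5.6).
- SAP 2.7 excludes missing data, not subjects with partial data. A device-related SAE already on record fails Device Success by its own definition.
- Mortality is protected for withdrawn subjects, because vital status is kept.
- The note on indirect information defines only what counts as contact with the subject. It does not stop a site from reporting a death or SAE learned from a relative, and Protocol 11.3 lists discharge summaries among adverse event source documents.
- Whether a subject is called missed or lost changes nothing in the analysis, since the SAP uses neither label.
- The primary endpoint is read at discharge, with day 10 as back-up, so a loss at day 30 does not touch it. The affected endpoints are descriptive.

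All of this stands, and it narrows the point. It does not answer three things: non-fatal events after withdrawal are outside the trial even when the subject agrees to follow-up; no vital-status check is required for a subject missing only day 30; and the SAP has no scoring rule for an incomplete 30-day composite.

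**Conclusion.** The point holds as a possible bias of limited size. Protocol 5.6 and SAP 2.7 together can leave the 30-day Device Success, Procedural Success, hospitalization and SAE results optimistic. The bound is 6.25 points for each subject without a day-30 result, reached only if there are no other failures, the subject is left out and the subject truly failed. If the subject truly succeeded, the available-case rate is equal or slightly low. The number of such subjects is unknown; the range of 1 to 3 is an assumption. Mortality is exposed only through the subject who misses day 30 without withdrawing. The change should be made because the subjects affected are plausibly informative, the trial is small and the remedy is cheap.

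**What to change.** 1. **Protocol 5.6, device-problem leavers.** Where the subject gives permission, record SAEs, re-intervention and status through day 30 on the CRF as trial data, and use them in the 30-day endpoints.
2. **Protocol 5.6, subject not reached at day 30.** After the calls and letter, obtain vital status and hospitalizations from a relative, the treating physician or discharge letters, with source documentation. Use them for mortality, hospitalization and SAE reporting. The definition of subject contact can stay as it is.
3. **SAP 2.7.** Count any failing component known before withdrawal or a missed visit, such as a device-related SAE or re-intervention, as failure of the 30-day composite even if the day-30 echo is missing. Report the number of subjects with complete 30-day data. Add a sensitivity analysis over all 16 with missing counted as failure.

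The lost-to-follow-up rule needs no rewording, since a new label recovers no data. Subjects who refuse further follow-up need not be scored as failures in the main analysis; the sensitivity analysis covers them.

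The cost is protocol and SAP wording, a permission line in the consent form, a few calls, and possibly slightly lower reported success rates.
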